9.9.2 Overall Survival Time

Definition: A measurement from the start of the treatment until death. Patients surviving are treated as censored at last date known alive.

9.9.3 Time to Remission

Definition: A measurement from the start of the treatment until the confirmed criteria for disease remission (PR + CR) are met. Patients not in remission are treated as censored at last date known alive.

9.9.4 Duration of Remission (Among Remitters, PR + CR)

Definition: A measurement from the earliest time when confirmed remission criteria are met until death or progression. Patients continuing in remission at the end of the study are treated as censored.

9.9.5 Follow-Up Time

Definition: The time from start of treatment until last date known alive among surviving patients with patients considered censored at death.

10. DRUG INFORMATION

Please refer to the latest version of the Investigator's Brochure (IB), provided as a document separate from this protocol.

10.1 Brentuximab vedotin

Brentuximab vedotin is a sterile, preservative-free, white to off-white lyophilized cake or powder supplied by Seattle Genetics in single-use vials for reconstitution for IV administration. Each vial of the product contains brentuximab vedotin (SGN-35), trehalose, sodium citrate, and polysorbate 80.

10.2 Clinical pharmacology

10.2.1 Mechanism of Action

Brentuximab vedotin is an ADC. The antibody is a chimeric IgG1 directed against CD30. The small molecule, MMAE, is a microtubule disrupting agent. MMAE is covalently attached to the antibody via a linker. Nonclinical data suggest that the anticancer activity of brentuximab vedotin is due to the binding of the ADC to CD30-expressing cells, followed by internalization of the ADC-CD30 complex, and the release of MMAE via proteolytic cleavage. Binding of MMAE to tubulin disrupts the microtubule network within the cell, subsequently inducing cell cycle arrest and apoptotic death of the cells.

10.2.2 Pharmacodynamics

QT/QTc Prolongation Potential

The effect of brentuximab vedotin (1.8 mg/kg) on the QTc interval was evaluated in an open-label, single-arm study in 46 evaluable patients with CD30-expressing hematologic malignancies. Administration of brentuximab vedotin did not prolong the mean QTc interval >10 ms from baseline. Small increases in the mean QTc interval (<10 ms) cannot be excluded because this study did not include a placebo arm and a positive control arm.

10.2.3 Pharmacokinetics

The pharmacokinetics of brentuximab vedotin were evaluated in phase 1 trials and in a population pharmacokinetic analysis of data from 314 patients. The pharmacokinetics of

three analytes were determined: the ADC, MMAE, and total antibody. Total antibody had the greatest exposure and had a similar PK profile as the ADC. Hence, data on the PK of the ADC and MMAE have been summarized.

Absorption

Maximum concentrations of ADC were typically observed close to the end of infusion. A multiexponential decline in ADC serum concentrations was observed with a terminal half-life of approximately 4 to 6 days. Exposures were approximately dose proportional from 1.2 to 2.7 mg/kg. Steady-state of the ADC was achieved within 21 days with every 3-week dosing of brentuximab vedotin, consistent with the terminal half-life estimate. Minimal to no accumulation of ADC was observed with multiple doses at the every 3-week schedule.

The time to maximum concentration for MMAE ranged from approximately 1 to 3 days. Similar to the ADC, steady-state of MMAE was achieved within 21 days with every 3 week dosing of brentuximab vedotin. MMAE exposures decreased with continued administration of brentuximab vedotin with approximately 50% to 80% of the exposure of the first dose being observed at subsequent doses.

Distribution

In vitro, the binding of MMAE to human plasma proteins ranged from 68–82%. MMAE is not likely to displace or to be displaced by highly protein-bound drugs. *In vitro*, MMAE was a substrate of P-gp and was not a potent inhibitor of P-gp.16

In humans, the mean steady state volume of distribution was approximately 6–10 L for ADC.

Metabolism

In vivo data in animals and humans suggest that only a small fraction of MMAE released from brentuximab vedotin is metabolized. *In vitro* data indicate that the MMAE metabolism that occurs is primarily via oxidation by CYP3A4/5. *In vitro* studies using human liver microsomes indicate that MMAE inhibits CYP3A4/5 but not other CYP isoforms. MMAE did not induce any major CYP450 enzymes in primary cultures of human hepatocytes.

Elimination

MMAE appeared to follow metabolite kinetics, with the elimination of MMAE appearing to be limited by its rate of release from ADC. An excretion study was undertaken in patients who received a dose of 1.8 mg/kg of brentuximab vedotin. Approximately 24% of the total MMAE administered as part of the ADC during a brentuximab vedotin infusion was recovered in both urine and feces over a 1-week period. Of the recovered MMAE, approximately 72% was recovered in the feces and the majority of the excreted MMAE was unchanged.

10.3 Supplier

Brentuximab vedotin will be supplied by Seattle Genetics. Please see Study Procedures Manual for instructions on ordering initial and subsequent drug supply shipments.

10.4 Preparation

Brentuximab vedotin vials are provided via single-use containers. Any partially used vials or diluted dosing solutions should be discarded using appropriate institutional drug disposal procedures.

Brentuximab vedotin should be reconstituted with the appropriate amount of Sterile Water for Injection, United States Pharmacopeia (USP) (or equivalent; see Pharmacy Manual for details). The vial should be gently swirled until the contents are completely dissolved. The vial must not be shaken or vigorously swirled; excess agitation may cause aggregate formation. The reconstituted drug product should be inspected visually for any particulate matter and discoloration.

The required volume of reconstituted drug product should be transferred to an infusion bag. There are no known incompatibilities between brentuximab vedotin and polyvinylchloride (PVC) ethylene vinyl acetate (EVA), polyolefin, or polyethylene bags. The reconstituted drug product should be diluted (see Pharmacy Manual for details) and the bag should be gently inverted to mix the solution. The bag must not be shaken; excess agitation may cause aggregate formation. Prior to administration, the reconstituted and diluted drug product should be inspected visually for any particulate matter and discoloration.

Detailed drug preparation instructions are provided in the Pharmacy Manual.

10.5 Storage and Handling

Refrigeration should be set at 2-8°C for storage of vials and solutions containing brentuximab vedotin. The controlled location must be accessible only to the pharmacist, the investigator, or a designated person. Brentuximab vedotin (SGN-35) for Injection does not contain preservatives; therefore, from a microbiological standpoint, opened and reconstituted vials of brentuximab vedotin should be used immediately. If not used immediately, the in-use storage should not be longer than 24 hours. It is recommended that brentuximab vedotin vials and solutions be stored protected from direct sunlight until the time of use. Reconstituted vials must not be shaken.

Drug accountability instructions are provided in the Study Procedures Manual.

10.6 Packaging and Labeling

Vialed drug product may be labeled as brentuximab vedotin, the United States adopted name (USAN) and the International Nonproprietary Name (INN), or as SGN-35, the compound code; the 2 names can be used interchangeably.

10.7 Dispensing

Brentuximab vedotin must be dispensed only from official study sites and to eligible subjects under the supervision of the site investigator. Brentuximab vedotin should be stored in a secure area according to local regulations. It is the responsibility of the site investigator to ensure that study drug is only dispensed to subjects.

10.8 Adverse Events

The following serious adverse reactions are discussed in greater detail in other sections of the prescribing information:

- Peripheral Neuropathy [see *Warnings and Precautions (10.9.1)*]
- Anaphylaxis and Infusion Reactions [see *Warnings and Precautions (10.9.2)*]
- Hematologic Toxicities [see *Warnings and Precautions (10.9.3)*]
- Serious Infections and Opportunistic Infections [see *Warnings and Precautions (10.9.4)*]
- Tumor Lysis Syndrome [see *Warnings and Precautions (10.9.5)*]
- Increased Toxicity in the Presence of Severe Renal Impairment [see *Warnings and Precautions (10.9.6)*]
- Increased Toxicity in the Presence of Moderate or Severe Hepatic Impairment [see *Warnings and Precautions (10.9.7)*]
- Hepatotoxicity [see *Warnings and Precautions (10.9.8)*]
- Progressive Multifocal Leukoencephalopathy [see *Warnings and Precautions (10.9.9)*]
- Pulmonary Toxicity [see *Warnings and Precautions (10.9.10)*]
- Serious Dermatologic Reactions [see *Warnings and Precautions (10.9.11)*]
- Embryo-Fetal Toxicity [see *Warnings and Precautions (10.9.12)*]

Please refer to the most current IB or package insert(s) for the comprehensive list of adverse events.

10.9 WARNINGS AND PRECAUTIONS

10.9.1 Peripheral Neuropathy

ADCETRIS treatment causes a peripheral neuropathy that is predominantly sensory. Cases of peripheral motor neuropathy have also been reported. ADCETRIS-induced peripheral neuropathy is cumulative. In the HL and sALCL clinical trials, 54% of patients experienced any grade of neuropathy. Of these patients, 49% had complete resolution, 31% had partial improvement, and 20% had no improvement. Of the patients who reported neuropathy, 51% had residual neuropathy at the time of their last evaluation. Monitor patients for symptoms of neuropathy, such as hypoesthesia, hyperesthesia, paresthesia, discomfort, a burning sensation, neuropathic pain, or weakness. Patients experiencing new or worsening peripheral neuropathy may require a delay, change in dose, or discontinuation of ADCETRIS [see *Dose Modification (6.1)*].

10.9.2 Anaphylaxis and Infusion Reactions

Infusion-related reactions, including anaphylaxis, have occurred with ADCETRIS. Monitor patients during infusion. If anaphylaxis occurs, immediately and permanently discontinue administration of ADCETRIS and administer appropriate medical therapy. If an infusion-related reaction occurs, the infusion should be interrupted and appropriate medical management instituted. Patients who have experienced a prior infusion-related

reaction should be premedicated for subsequent infusions. Premedication may include acetaminophen, an antihistamine, and a corticosteroid.

10.9.3 Hematologic Toxicities

Prolonged (≥ 1 week) severe neutropenia and Grade 3 or Grade 4 thrombocytopenia or anemia can occur with ADCETRIS. Febrile neutropenia has been reported with treatment with ADCETRIS. Complete blood counts should be monitored prior to each dose of ADCETRIS and more frequent monitoring should be considered for patients with Grade 3 or 4 neutropenia. Monitor patients for fever. If Grade 3 or 4 neutropenia develops, consider dose delays, reductions, discontinuation, or G-CSF prophylaxis with subsequent ADCETRIS doses [see *Dose Modification (6.1)*].

10.9.4 Serious Infections and Opportunistic Infections

Serious infections and opportunistic infections such as pneumonia, bacteremia, and sepsis or septic shock (including fatal outcomes) have been reported in patients treated with ADCETRIS. Patients should be closely monitored during treatment for the emergence of possible bacterial, fungal, or viral infections.

10.9.5 Tumor Lysis Syndrome

Patients with rapidly proliferating tumor and high tumor burden may be at increased risk of tumor lysis syndrome. Monitor closely and take appropriate measures.

10.9.6 Increased Toxicity in the Presence of Severe Renal Impairment

The frequency of \geq Grade 3 adverse reactions and deaths was greater in patients with severe renal impairment compared to patients with normal renal function. Due to higher MMAE exposure, \geq Grade 3 adverse reactions may be more frequent in patients with severe renal impairment compared to patients with normal renal function. Avoid the use of ADCETRIS in patients with severe renal impairment [creatinine clearance (CL_{cr}) <30 mL/min].

10.9.7 Increased Toxicity in the Presence of Moderate or Severe Hepatic Impairment

The frequency of \geq Grade 3 adverse reactions and deaths was greater in patients with moderate and severe hepatic impairment compared to patients with normal hepatic function. Avoid the use of ADCETRIS in patients with moderate (Child-Pugh B) or severe (Child-Pugh C) hepatic impairment.

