 6. Patients with late relapse (>2 years) of non seminomatous germ cell tumors are eligible if they have received first line platinum based chemotherapy and their recurrence is not amenable to surgical resection based on the treating physician expert opinion.
 7. Patients with brain metastases are allowed onto the study as long as patients have completed their treatment for brain metastasis, no longer require corticosteroids, and are asymptomatic. Subjects with neurological symptoms should undergo a head CT scan or brain MRI to exclude brain metastasis, at the discretion of the treating physician.
 8. Patients with ECOG performance status of 0-2.
 9. Adequate organ and marrow function as defined below:
 - a. Hemoglobin ≥ 8 g/dL
 - b. Absolute neutrophil count $\geq 1,000/\text{mm}^3$
 - c. Platelet count $\geq 75,000/\text{mm}^3$
 - d. Total bilirubin $\leq 1.5 \times \text{ULN}$ except patients with documented Gilbert's syndrome ($\leq 3 \times \text{ULN}$)
 - e. Alanine aminotransferase (ALT) and aspartate aminotransferase (AST) $\leq 2.5 \times \text{ULN}$; for patients with hepatic metastases, ALT and AST $\leq 5 \times \text{ULN}$
 - f. Calculated creatinine clearance ≥ 30 mL/min as determined by the Cockcroft-Gault equation.
 10. Patients who are willing and able to comply with the protocol and study procedures including willingness to undergo tumor biopsy for tumor cells before therapy to assess for CD30 status (unless archival tumor tissue from orchiectomy or other previous sample is not obtainable despite efforts to do so and a fresh tumor biopsy is not feasible).
 11. Females of childbearing potential must not be pregnant or breast-feeding. Male and female patients of reproductive potential must agree to use *two forms* of highly effective contraception from the screening visit through 28 days after the

last dose of study drug unless patient is practicing true abstinence. Acceptable forms of effective contraception include:

- Oral, injected or implanted hormonal methods of contraception.
- Tubal ligation
- Placement of an intrauterine device (IUD) or intrauterine system (IUS).
- Barrier methods of contraception: Condom or Occlusive cap (diaphragm or cervical/vault caps) with spermicidal foam/gel/film/cream/suppository.
- Male sterilization (defined as complete retrograde ejaculation or the appropriate post-vasectomy documentation of the absence of sperm in the ejaculate).

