- True abstinence: When this is in line with the preferred and usual lifestyle of the subject. [Periodic abstinence (e.g., calendar, ovulation, symptothermal, post-ovulation methods) and withdrawal are not acceptable methods of contraception.]

Pregnancy tests for females of childbearing potential are required; must be serum at screening and the post treatment safety assessment visit. A positive urine pregnancy test must be confirmed by a serum pregnancy test and a pelvic US since some NSGCT may secrete beta-hCG and cause a false positive pregnancy. A pelvic US does not need to be repeated with each cycle unless the treating physician thinks it is necessary to do so.

12. Potential subject must have the ability to understand (as judged by the treating physician) and willingness to provide written informed consent and HIPAA authorization for release of personal health information.

NOTE: HIPAA authorization may be included in the informed consent or obtained separately. Written informed consent must be obtained from a potential subject prior to the conduct of any study-specific procedures.

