3.2 Exclusion Criteria

Subjects meeting any of the criteria below may not participate in the study:

1. Patients with pure seminoma.
2. Patients with pure teratoma.
3. Chemotherapy within 2 weeks of initiating study treatment. There is no maximum allowable number of previous therapies.
4. Major surgery within 3 weeks of starting study treatment. There is no minimum time requirement for minor procedures such as biopsy or vascular access placement.
5. Radiation within 2 weeks of starting study treatment.
6. \geq Grade 3 neuropathy at the time of enrollment.
7. Pregnancy or breast-feeding.
8. Previous treatment with any anti-CD30 directed therapy.

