4. SUBJECT REGISTRATION

All patients will be registered with the Indiana University Cancer Center Clinical Trials Office. Regulatory files will be maintained by the Clinical Trials Office. Applicable regulatory documents must be completed and on file prior to registration of any patients. Potential patients will be identified in the Oncology outpatient clinics or by referrals from outside physicians. Patients who appear to be eligible for this trial will undergo the Informed Consent Process and be screened for eligibility utilizing the Eligibility Criteria. The original signed IRB approved Informed Consent Document and completed eligibility checklist will be forwarded to the Clinical Trials Office designee for eligibility verification and registration in the OnCore[®] database. Notification will be sent to the principal investigator, treating physician and research nurse when registration is complete to confirm registration and inform them of patient ID number.

Study data will be collected and stored in OnCore[®], developed by Forte Research Systems, Inc. (www.forteresearch.com). OnCore[®] Enterprise Research is a comprehensive, web-based, Clinical Trial Management System (CTMS) which utilizes an Oracle database. It has been licensed by Indiana University (IU) to support the operations and data capture of clinical research trials.

The system has been installed and configured within a HIPAA-aligned, Information Technology (IT), operations center supported by IU's IT organization, University Information Technology Services (UITS). OnCore[®] provides users secure access with unique IDs/passwords and restricts access by assigned roles, from any location, to record, manage, and report on data associated with the operation and conduct of clinical trials.

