5. TREATMENT PLAN

- Eligible patients will be divided into two cohorts, those who are CD30 positive and those who are CD30 negative/unknown. Both groups will be treated similarly and in parallel but analyzed separately.
- CD30 status may be unknown in the unlikely case of tumor-marker-only relapse or when a fresh tumor biopsy is not feasible, and archival tumor tissue is not obtainable

despite efforts to do so. These patients will be included in the CD30 negative cohort for analysis purposes, since statistically NSGCT are more likely to be CD30 negative.

The number of such patients with unknown CD30 status should not exceed 5 patients.

- Enrollment to the study does not have to wait for determination of CD30 status prior to treatment, unless in the situation where one arm is closed for enrollment or an interim assessment of response for the Simon stage I phase is needed. For example:
 - The first 10 patients can enroll on the study and start on therapy without waiting for CD30 status assessment. Prior to enrolling patient number 11, CD30 status need to be determined for all patients to make sure an interim assessment of response for the Simon stage I phase is not needed (i.e. one arm is at 10 patients).
 - If an arm has closed for lack of efficacy, CD30 status need to be assessed prior to starting therapy to make sure that patients belong to the open arm.
 - If both arms advance to the second stage of the Simon design then enrollment can again be pursued without waiting for CD30 status until one arm is closed to accrual.
- Eligible patients will be treated with brentuximab vedotin at 1.8 mg/kg IV every 3 weeks (maximum dose of 180 mg) indefinitely until disease progression, unacceptable toxicity, or study closure.
- Eligible patients with grade 2 peripheral neuropathy at enrollment will be treated with brentuximab vedotin at 1.2 mg/kg IV every 3 weeks (maximum dose of 180 mg) indefinitely until disease progression, unacceptable toxicity, or study closure.
- Response to treatment will be assessed clinically with history, physical exam and tumor markers measurement (BHCG and AFP) on day 1 of each cycle and with CT scans after cycle 2, 4, and every 4 cycles thereafter while receiving treatment.

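### The warning to avoid the drug in Child-Pugh B or C hepatic impairment is only partly carried into the eligibility criteria, although the matching renal warning is carried exactly

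*Combined protocol and SAP*

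**What the plan says.** Section 10.9.7 states: "Avoid the use of ADCETRIS in patients with moderate (Child-Pugh B) or severe (Child-Pugh C) hepatic impairment". It reports that reactions of grade 3 or higher, and deaths, were more common in moderate and severe hepatic impairment than with normal liver function. Section 10.9.8 adds that hepatotoxicity has been fatal, has occurred after the first dose, and may be more likely with preexisting liver disease.

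In Section 3.1, item 9 sets the organ-function limits:

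- Item 9d caps total bilirubin at 1.5 × ULN. The exception ("except patients with documented Gilbert") raises the cap to 3 × ULN in that syndrome.
- Item 9e caps ALT and AST at 2.5 × ULN. The allowance ("for patients with hepatic metastases, ALT and AST") goes up to 5 × ULN.
- Item 9f requires a creatinine clearance of at least 30 "mL/min as determined by the Cockcroft-Gault equation".

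Section 3.2 opens with "Subjects meeting any of the criteria below may not participate in the study" and lists eight items. None mentions liver disease, cirrhosis or Child-Pugh class.

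Section 4 says that patients who appear eligible are "screened for eligibility utilizing the Eligibility Criteria", and that a completed checklist goes for verification. Section 14.3 repeats the central check for participating sites. Section 5 then says: "Eligible patients will be treated with brentuximab vedotin at 1.8 mg/kg IV every 3 weeks". The only reduced starting dose is for grade 2 neuropathy at enrollment.

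**The concern.** Section 10.9 contains two warnings that tell the physician to avoid the drug in a class of patients: renal (10.9.6) and hepatic (10.9.7). The renal one became an entry criterion. The hepatic one did not, and the protocol gives no reason for treating them differently. Enrollment in this multicenter trial is decided and verified against Section 3, so a limit that appears only in the drug-information section may not be applied when a patient is registered.

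What is at stake is patient safety: the warning concerns severe reactions and death. Because hepatotoxicity has been seen after the first dose, chemistry drawn at each cycle cannot fully replace a check at entry. Nothing here bears on the response-rate hypotheses, the stopping rule or the sample size.

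**Working it through.** The plan states no figure on this point, so the check compares the two warnings with the criteria and then asks whether the existing caps already imply the hepatic limit.

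**Step 1. Warnings against criteria**

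| Warning | Patients to avoid | Entry criterion | Match |
|---|---|---|---|
| 10.9.6, renal | Creatinine clearance below 30 mL/min | 9f: at least 30 mL/min | Exact complement |
| 10.9.7, hepatic | Child-Pugh B or C | 9d (bilirubin) and 9e (ALT/AST) | Partial |

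Sections 10.9.1 to 10.9.12 contain two warnings of this kind, and one of the two is carried exactly into Section 3. Child-Pugh is mentioned only in 10.9.7.

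**Step 2. Assumptions not in the documents**

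- Usual Child-Pugh scoring: bilirubin, albumin, INR, ascites and encephalopathy, each 1 to 3 points. Class A is 5–6, B is 7–9 and C is 10–15.
- Bilirubin below 2 mg/dL scores 1, from 2 to 3 scores 2, and above 3 scores 3.
- Bilirubin ULN of 1.0 to 1.3 mg/dL.

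ALT and AST are not among the five components, so 9e does not determine the class.

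**Step 3. Ordinary patients under 9d**

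Cap = 1.5 × ULN: 1.5 × 1.0 = 1.50 mg/dL up to 1.5 × 1.3 = 1.95 mg/dL. All values are below 2, so bilirubin scores 1 point throughout the range.

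Class B starts at 7, so it needs 7 − 1 = 6 or more points from the other four components, whose minimum is 4. Item 9 limits none of them. For example, bilirubin 1 + albumin 3 + ascites 2 + INR 1 + encephalopathy 1 = 8, which is class B with bilirubin and transaminases inside their caps.

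Suppose bilirubin scores 1 and there is no encephalopathy (1 point). The 3 × 3 × 3 = 27 combinations of albumin, INR and ascites then split into 4 class A, 19 class B and 4 class C. These count score patterns and say nothing about how often such patients occur. They show only that the bilirubin cap does not imply class A.

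**Step 4. Patients with Gilbert's syndrome under 9d**

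Cap = 3 × ULN, with the other four components normal (4 points):

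| ULN (mg/dL) | Cap (mg/dL) | Bilirubin points | Total | Class |
|---|---|---|---|---|
| 1.0 | 3.0 | 2 | 2 + 4 = 6 | A |
| 1.1 | 3.3 | 3 | 3 + 4 = 7 | B |
| 1.2 | 3.6 | 3 | 3 + 4 = 7 | B |
| 1.3 | 3.9 | 3 | 3 + 4 = 7 | B |

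A bare Child-Pugh exclusion would therefore bar some patients whom 9d deliberately admits. This determines how the fix must be worded.

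**Step 5. What screening collects**

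Section 7.1.1 requires history, examination, CT and a metabolic panel. The analytes it names do not include albumin, though the list is not exhaustive and the panel may contain it. No clotting test is listed. Section 9.1.3 mentions ascites only as non-measurable disease.

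**The case against.** The strongest reply is that 10.9.7 is itself protocol text, and Section 13.2 requires the study to be run as the approved protocol describes. An investigator can apply item 9 and then the warning, so the two sections do not conflict. Section 5 fixes dose and schedule; it does not oblige anyone to treat a patient whom the warning covers. The liver was plainly considered, since 9d and 9e carry specific allowances, and a single laboratory threshold such as creatinine clearance transfers into a criterion more easily than a composite class. ECOG 0–2, capacity to consent, history, examination and CT will screen out many patients with advanced liver disease. Table 1 and 10.9.8 provide for withholding or changing treatment afterwards. Finally, the carve-outs exempt the Gilbert's case and tumor-related ascites or low albumin, so the proposed exclusion would apply to few patients and still rests on the investigator's judgment.

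Much of this stands. There is no contradiction, the affected group is narrow, and naming albumin is a small clarification. The eligibility checklist is not in the documents, so that it mirrors Section 3 is an inference. But these safeguards reduce the gap without closing it: none states the 10.9.7 limit at the point where eligibility is decided, and no dose rule covers hepatic impairment at baseline. On-treatment rules act only after exposure. The renal warning was equally available to investigators in Section 10, and the protocol still made it an entry criterion.

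**Conclusion.** The concern holds. The hepatic warning is only partly reflected in Section 3, the renal one is reflected exactly, and a patient in Child-Pugh class B or C can meet the eligibility criteria as written. The textual comparison rests on the protocol alone. That a patient within 9d and 9e can be class B rests on the usual Child-Pugh scoring. The point values also use a bilirubin ULN of 1.0 to 1.3 mg/dL, but the gap does not depend on the exact ULN, because no criterion covers albumin, INR, ascites or encephalopathy.

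The documents give no frequency of hepatic impairment in this population, so the number affected is unknown; it is probably small. This is a safety point that should be corrected. It has no demonstrated effect on the design or analysis.

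**What to change.** Add one exclusion to Section 3.2: *known moderate or severe hepatic impairment (Child-Pugh B or C)*. State that neither of the following excludes a patient by itself:

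1. isolated raised bilirubin from documented Gilbert's syndrome within the item 9d limit;
2. ascites or low albumin that the investigator attributes to tumor rather than to liver dysfunction.

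The first keeps the exclusion consistent with 9d. The second avoids excluding patients for a disease site that Section 9.1.3 recognizes.

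Assess the criterion from the history, examination, metabolic panel and baseline CT already required at screening. Name albumin in the panel, and request INR only where liver disease is suspected. Leave items 9d and 9e as they are.

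The cost is one line with two carve-outs, a named analyte and an occasional INR. A few patients may be lost to enrollment. That number cannot be estimated from the documents, but they are patients for whom 10.9.7 already advises against the drug.
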